5 TREATMENT AND ASSESSMENT

Delivery of the WRAPSODY stent graft will be according to the procedure in Appendix B.

Visit Schedule

Visit 1:

- Screening
 - Informed consent
 - Eligibility criteria assessment
 - Demographics
 - Vital Signs
 - Medical History relevant to dialysis:
 - Type, location and date of all previous venous outflow circuit intervention(s)
 - Prior dialysis access type(s)
 - Location of current dialysis access (AVF/AVG)
 - For subjects with AV fistula, date fistula was first used for dialysis
 - For subject with AV graft, date of graft creation
 - Clinical reason(s) subject was referred for obstruction evaluation
 - Targeted physical exam, including at a minimum the following Clinical Indicators of Obstruction:
 - Assessment of edema in hand, arm, neck, head or trunk
 - Pain related to dialysis circuit
 - Respiratory symptoms
 - Neurological symptoms
 - Skin changes
 - Concurrent medical conditions
 - Concomitant medications

- Serum pregnancy test, if applicable
- Angiographic Imaging with location, length and percent stenosis of target lesion
- Doppler ultrasound to be performed prior to procedure
 - NOTE: A doppler ultrasound must be attempted for each subject prior to the study procedure. However, if doppler ultrasound results are unobtainable in some cases due to lesion location, this will not be considered a protocol violation.
- Study procedure (WRAPSODY Stent Graft Placement)
 - Length and diameter of stent graft
 - Percent residual stenosis
 - Doppler ultrasound post stent graft placement
 - NOTE: A doppler ultrasound must be attempted for each subject after the study procedure. However, if doppler ultrasound results are unobtainable in some cases due to lesion location, this will not be considered a protocol violation.
 - Adverse event review
 - Investigator's assessment of technical success (defined as successful deployment at intended location)
 - Procedural medications

Visit 2: 30 days (\pm 7 days)

- Targeted physical exam, including at a minimum the following Clinical Indicators of Obstruction:
 - Assessment of edema in hand, arm, neck, head or trunk
 - Pain related to dialysis circuit
 - Respiratory symptoms
 - Neurological symptoms
 - Skin changes
- Hemodialysis adequacy at the first session following the study procedure
- Adverse event review
- Interventions on venous outflow circuit since last visit
- Concomitant medications

Visit 3: 3 months (± 4 weeks)

- Targeted physical exam, including at a minimum the following Clinical Indicators of Obstruction:
 - Assessment of edema in hand, arm, neck, head or trunk
 - Pain related to dialysis circuit
 - Respiratory symptoms
 - Neurological symptoms
 - Skin changes
- Adverse event review
- Interventions on venous outflow circuit since last visit
- Concomitant medications

Visit 4: 6 months (± 4 weeks)

- Targeted physical exam, including at a minimum the following Clinical Indicators of Obstruction:
 - Assessment of edema in hand, arm, neck, head or trunk
 - Pain related to dialysis circuit
 - Respiratory symptoms
 - Neurological symptoms
 - Skin changes
- Adverse event review
- Interventions on venous outflow circuit since last visit
- Concomitant medications

Visit 5: 12 months (± 8 weeks)

Traditional visit windows are being expanded for the 12-month visit to allow for potential impacts due to COVID-19.

- Targeted physical exam, including at a minimum the following Clinical Indicators of Obstruction:
 - Assessment of edema in hand, arm, neck, head or trunk
 - Pain related to dialysis circuit
 - Respiratory symptoms
 - Neurological symptoms
 - Skin changes
- Adverse event review
- Interventions on venous outflow circuit since last visit

- Concomitant medications
- X-rays of the treated area (subset of subjects with thoracic central venous target lesions only)
 - Minimum of two projections required to visualize WRAPSODY stent graft

Additional visits, as needed/referred for evaluation/treatment of venous outflow dysfunction

- Angiographic Evaluation, if medically indicated
- Clinical reason(s) subject was referred for obstruction evaluation
- Targeted physical exam, including at a minimum the following Clinical Indicators of Obstruction:
 - Assessment of edema in hand, arm, neck, head or trunk
 - Pain related to dialysis circuit
 - Respiratory symptoms
 - Neurological symptoms
 - Skin changes
- Interventions on venous outflow circuit since last visit
- Adverse event review
- Current intervention, if done, including:
 - Procedure type
 - Lesion location and length
 - % stenosis before treatment
 - % residual stenosis after treatment
- Concomitant medications
- X-rays of the treated area (subset of subjects with thoracic central venous target lesions only)
 - Subjects who were unable to have X-Rays completed at scheduled Visit 5 (12 Months) may be brought back for an additional visit to complete X-Rays after obtaining proper consent.

6 SUBJECT COMPLETION AND WITHDRAWAL

A subject is considered to have completed the study if he/she has had an initial study procedure and has follow-up information through 12 months.

Subjects will be informed that they have the right to withdraw from the study at any time for any reason, without prejudice to their medical care. The investigator also has the right to withdraw subjects from the

study for any reason. If a subject has a kidney transplant and/or current dialysis access is abandoned, he/she will be withdrawn from the study. If a subject is withdrawn from the study, the reason will be recorded on the end of study form. If a subject signs informed consent and is not enrolled in the study for any reason, the subject is a screen failure. A record of all subjects who signed an informed consent will be maintained.

Subjects will be considered lost to follow up if:

- The site has documented attempts to contact the subject at least three times without success, AND
- The site has a documented attempt to contact the subjects' dialysis center, AND
- The site has a documented attempt to contact the subjects' managing physicians

Subjects who are withdrawn from the study after completion of the study procedure for any reason will not be replaced. All subjects regardless of whether or not they complete the study, will be included in the Intent-to-Treat (ITT) population. The Sponsor may terminate the study at any time. In addition, termination or modification may be recommended for any other perceived safety concern based on clinical judgment of the Data Monitoring Committee (DMC) members.

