Stent grafts have been used to treat TCVO, but most reports cite their use within larger randomized clinical trials or in small cohort studies. In a study by Jones and colleagues, VIABAHN stent grafts were placed in the central veins of 42 subjects with stenosis that did not respond to PTA. Primary patency rates at 3, 6, 12, and 24 months were 97%, 81%, 67%, and 45%, respectively. Primary assisted patency rates at 3, 6, 12, and 24 months were 100%, 100%, 80%, and 75%. This suggests that stent grafts placed

for the treatment of central venous stenosis are an effective way to maintain luminal patency if PTA fails (Jones 2011).

As further support, in the RESCUE study summarized earlier, a subset of 73 subjects (total study n = 275) with stenoses in the central vein (n=41), subclavian vein (n=30), brachiocephalic vein (n=1), and superior vena cava (n=1) demonstrated statistically significantly better primary patency in the treatment area at 24 months for the stent graft group vs PTA (13.6% vs 4.3%, p < .001).

To date there have been no large prospective randomized studies to investigate stent graft performance in the central veins.

Stent grafts used in central veins are the GORE VIABAHN, FLUENCY PLUS and the FLAIR Endovascular Stent Graft. Per these products' Instructions for Use, the VIABAHN stent graft is a flexible, self-expanding endoluminal endoprostheses consisting of an expanded polytetrafluoroethylene (ePTFE) lining with an external nitinol support extending along its entire length. The FLUENCY PLUS is a flexible self-expanding vascular prosthesis comprising ePTFE encapsulating a nitinol frame work, except for 2 mm at each of the flared stent graft ends with 4 radiopaque Tantulum markers. The inner lumen of the stent graft surface is carbon impregnated. The FLAIR Endovascular Stent Graft is a flexible, self-expanding endoprostheses comprising an expanded (ePTFE) encapsulating a nitinol stent framework. The nitinol stent, including distal and proximal ends, is encapsulated within the ePTFE and the inner lumen of the stent graft is carbon impregnated. The ePTFE outer wall of the stent graft, which contacts the AV access graft and native vein, contains cutouts which expose the nitinol stent.

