2.2 Secondary Objectives

- Proportion of subjects with Target Lesion Primary Patency at 3, 6 and 12 months
- Proportion of subjects with Assisted Primary Patency of the target lesion at 30 days, 3, 6 and 12 months
 - Time to loss of Assisted Primary Patency of the target lesion is defined as time following study procedure until uncorrectable target lesion occlusion
- Proportion of subjects with Primary Patency of the venous outflow circuit at 30 days, 3, 6, and 12months
 - Time to loss of Primary Patency of the venous outflow circuit is defined as the time following initial study procedure until the next venous outflow circuit intervention
- Proportion of subjects with Assisted Primary Patency of the venous outflow circuit at 30 days, 3, 6 and 12 months.

- Time to loss of Assisted Primary Patency of the venous outflow circuit is defined as the time following initial study procedure until complete access abandonment.
- Index of Patency Function at 3, 6 and 12 months, defined as time from initial study procedure to complete access abandonment divided by number of venous outflow circuit re-interventions to maintain hemodialysis
- Procedure or device related adverse events at 3, 6 and 12 months
- Clinical Success
 - The resumption of successful dialysis through existing access for at least one session following initial study procedure
- Anatomic Success
 - Less than 30% residual stenosis immediately following study procedure
- Procedural Success
 - The achievement of both clinical and anatomic success

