7.2 Adverse Event Reporting

The Investigators are responsible for monitoring the safety of subjects who have been enrolled in this study. All adverse events (AE) considered to be related to study procedure will be followed until the event resolves or has reached a final outcome. AEs will be evaluated for severity according to the following Common Terminology Criteria for Adverse Events (CTCAE) grading scale:

- Grade 1: Mild; asymptomatic or mild symptoms; clinical or diagnostic observations only; intervention not indicated.
- Grade 2: Moderate; minimal, local or noninvasive intervention indicated; limiting age appropriate instrumental ADL.
- Grade 3: Severe or medically significant but not immediately life-threatening; hospitalization or prolongation of hospitalization indicated; disabling; limiting self care ADL.
- Grade 4: Life-threatening consequences; urgent intervention indicated.
- Grade 5: Death related to AE.

The Investigator, based on his/her clinical judgment and the following definitions, must determine the relationship of the adverse event to the device and/or procedure:

- None: The AE/SAE does not follow reasonable temporal sequence from the time of study procedure and/or does not follow a known response pattern to the study procedure and is likely to have been produced by other factors.
- Possible: The AE/SAE follows a reasonable temporal sequence from the time of study procedure, and/or follows a known response pattern to the study procedure, but could have been produced by other factors.
- Probable: The AE/SAE follows a reasonable temporal sequence from the time of study procedure, follows a known response pattern to the study procedure, and cannot reasonably have been produced by other factors.
- Definite: The AE/SAE follows a reasonable temporal sequence from the time of study procedure; follows a known response pattern to the study procedure; and cannot have been produced by other factors.

Investigators are required to document all device and/or study procedure related AEs occurring during the study commencing with the date of study procedure through the protocol defined 12 month post-treatment follow-up period, or discontinuation, death, or loss to follow-up subject. AEs that occur following the signature of informed consent but prior to treatment will not be captured.

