7.3 Serious Adverse Event Reporting

Any unanticipated adverse event or SAE that occurs during study procedure through the 12 month follow-up period, whether or not related to the study procedures, must be reported to the Sponsor within 24 hours of site knowledge of the event on the electronic SAE form. The SAE must be completely described on the AE CRF as well as the electronic SAE report form.

Safety Contact Information:
[REDACTED]
[REDACTED]
[REDACTED]

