12 PROTOCOL COMPLIANCE

The Investigators will conduct the trial in compliance with the protocol provided by Merit Medical Systems. Modifications to the protocol must not be made without agreement of the Investigator and Merit Medical Systems. Changes to the protocol potentially affecting safety or efficacy will require written EC approval/favorable opinion prior to implementation, except when the modification is needed to eliminate an immediate hazard(s) to subjects. Any deviations from the protocol must be captured on the electronic protocol deviation form and reported to EC and any other regulatory authorities as applicable.

DCO20-036_09OCT2020

Confidential

Page 25 of 34

Effort should be made to have subjects return to study physician office for in-person follow-up visits, but if subjects are unable or unwilling to complete visits the clinical trial site may obtain subject status information from the subject's dialysis center or other treating physician. The clinical trial site will confirm with subjects' dialysis centers whether any access or venous outflow dysfunction revisions have happened at other facilities.

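### Withdrawal at access abandonment or transplant ends capture of new related adverse events on the retained implant, although related events at 12 months are a secondary endpoint

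*Combined protocol and SAP*

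**What the plan says.** - Section 6: "If a subject has a kidney transplant and/or current dialysis access is abandoned, he/she will be withdrawn from the study". Subjects withdrawn after the procedure are not replaced.
- Section 7.2: sites document related AEs from the procedure through "the protocol defined 12 month post-treatment follow-up period, or discontinuation, death, or loss to follow-up subject". AEs "considered to be related to study procedure will be followed until the event resolves or has reached a final outcome".
- Section 7.1 asks for AEs over the 12-month follow-up period to be recorded. Section 7.3 requires expedited reporting of any SAE "that occurs during study procedure through the 12 month follow-up period, whether or not related to the study procedures". Neither mentions subjects who have been withdrawn.
- Section 2.2 lists "Procedure or device related adverse events at 3, 6 and 12 months" among the secondary objectives. It also makes complete access abandonment the event that ends assisted primary patency of the venous outflow circuit.
- Section 9 puts every treated subject in the safety population and describes the analysis as descriptive, with confidence intervals. It gives no denominator, censoring rule or exposure adjustment for the related-AE endpoint; the secondary endpoints it names are all patency endpoints.
- Section 12 allows remote ascertainment: "the clinical trial site may obtain subject status information from the subject's dialysis center or other treating physician". Footnote 3 of Appendix A says much the same.

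**The concern.** One of the trial's own outcomes, abandonment, triggers removal from the study, and removal ends the recording of new related AEs. The stent graft does not leave the body because the access is no longer used. An infection, migration or explant arising afterwards would not be documented under Section 7.2, and no section provides safety-only follow-up. Section 7.1 adds to this by not counting venous outflow obstructions as AEs: a subject whose access fails by obstruction contributes no AE for that failure and then leaves AE collection.

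At stake is how complete the 12-month safety description of a first-in-human implant is. Section 8 also ties a committee meeting to any SAE or unanticipated device effect that leads to surgery or death. Whether such an event after abandonment would reach the committee depends on which of Sections 7.2 and 7.3 a site follows.

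**Working it through.** **Step 1: read the passages together.** Abandonment or transplant leads to withdrawal (Section 6). Withdrawal is a discontinuation, so documentation of related AEs ends (Section 7.2). Follow-up to resolution in 7.2 covers events already open, not new ones. Sections 7.1 and 7.3 run to 12 months without exception, but set no contacts for withdrawn subjects and do not say that they override the cut-off in 7.2. The passages conflict.

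**Step 2: direction.** The plan gives no abandonment, transplant or AE rate, so there is no figure to reproduce. Let *p* be the 12-month related-AE risk on study, *w* the 12-month risk of abandonment or transplant, and *r* the AE hazard after withdrawal divided by that before. All three are assumptions. With constant hazards a = −ln(1 − p) and b = −ln(1 − w), the crude proportion over all treated subjects is

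observed = a/(a + b) × [1 − exp(−(a + b))].

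For p = w = 20%, a = b = 0.2231, so observed = 0.5 × (1 − 0.64) = 18.0%.

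| w (p = 20%) | Observed | True, r = 1 | True, r = 3 |
|---|---|---|---|
| 5% | 19.5% | 20.0% | 20.8% |
| 20% | 18.0% | 20.0% | 23.2% |
| 30% | 16.9% | 20.0% | 24.9% |

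If r = 0 the observed and true values agree (18.0% at w = 20%). On this denominator the shortfall is zero or positive. Other estimators behave differently at p = w = 20%:
- Dropping withdrawn subjects without an AE from the denominator gives 0.18/(1 − 0.18) = 22.0%. That is above the true 20.0% if r = 1 and below 23.2% if r = 3.
- A Kaplan-Meier estimate censored at withdrawal gives 20.0%: right for r = 1, low for r = 3 (true 23.2%), high for r = 0 (true 18.0%).

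**Step 3: person-time.** The only anchor is the 42-subject central-vein stent-graft series in Section 1.3: "Primary assisted patency rates at 3, 6, 12, and 24 months were 100%, 100%, 80%, and 75" per cent. All losses up to 12 months fall after month 6. If evenly spread, they average month 9, with 3 months remaining. Taking loss of assisted patency as abandonment (assumption), 20% of 50 is 10 subjects; 5 is taken as a lower value without a source.
- 10 × 3/12 = 2.5 patient-years; 2.5/50 = 5%.
- 5 × 3/12 = 1.25 patient-years; 1.25/50 = 2.5%.

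**Step 4: missed subjects if exit is at month 9.** Expected number = leavers × (AE-free to month 9) × (AE in the last 3 months). With p = 20% the hazard is 0.2231 per year and AE-free to month 9 is exp(−0.2231 × 0.75) = 0.846.
- r = 1: 10 × 0.846 × [1 − exp(−0.0558)] = 10 × 0.846 × 0.0543 = 0.46 subjects, or 0.9 percentage points of 50.
- r = 3: 10 × 0.846 × [1 − exp(−0.1674)] = 10 × 0.846 × 0.1541 = 1.30 subjects, or 2.6 points.
- With 5 leavers these halve to 0.23 and 0.65 subjects.

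The table in Step 2 spreads withdrawals over the whole year and so gives larger losses (about 10% of person-time at w = 20%). The cited series does not support that timing.

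**The case against.** The strongest defence is that the data are less incomplete than Section 6 alone suggests. Related AEs already open are followed to an outcome. Events before or at abandonment are counted, and abandonment itself is a patency event. Sections 7.1 and 7.3 can be read as keeping AE and SAE recording alive to 12 months. Primary safety is at 30 days, access expected to be abandoned within 3 months is excluded (Section 3.2), and Section 4 calls later follow-up supplementary. No comparison is made. At an AE risk of 20% and n = 50 the 95% interval has a half-width of 1.96 × √(0.2 × 0.8/50) = 11 points, well above the shortfalls in Step 4.

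Most of this stands and limits the size. It does not close the gap: no section arranges contact after withdrawal, 7.2 says that documentation stops, and estimates with intervals are all that a descriptive study produces. Sampling error is also reported in an interval; missed events are not.

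A reader might infer more than the documents support:
- **That nothing is captured after withdrawal.** Only new events are at issue, and for SAEs the sections conflict.
- **That the bias is certainly downward.** This holds only for the crude proportion over all treated subjects. It is zero if there is no hazard after exit, and the plan names no estimator.
- **That all lost time comes from the highest-risk subjects.** No passage gives AE risk after abandonment, and transplant is not access failure.
- **That 6-month results are distorted, or that up to 10% of person-time is lost.** The cited series lost no assisted patency by month 6. An average of 6 months remaining would need every loss to fall right after month 6.
- **That withdrawn subjects drop out of the X-ray subset.** Section 5 permits late X-ray visits and does not say whether withdrawn subjects qualify.

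**Conclusion.** The point holds as a gap in safety ascertainment and a conflict between Section 7.2 and Sections 7.1 and 7.3. Read with Section 6, the plan stops recording new related AEs on a retained implant at abandonment or transplant while keeping a 12-month related-AE endpoint. Over all treated subjects, the crude 12-month proportion is then equal to or below its true value.

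The size cannot be derived from the documents. Under the month-9 assumption it is 2.5 to 5% of planned person-time and, at an assumed AE risk of 20%, about 0.2 to 1.3 missed subjects of 50 for post-exit hazards one to three times the on-study hazard. The series behind that assumption is a loose proxy: it covers central veins only, in stenoses that did not respond to angioplasty, and loss of assisted patency is not the same as abandonment. Transplants have no input at all. The effect is mainly on the 12-month result; the 30-day primary endpoint is little affected. It is worth correcting because the remedy is cheap, not because the bias is shown to be large.

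**What to change.** 1. Section 6: make abandonment or transplant end patency follow-up only, with the event and its date recorded. Continue AE, SAE, explant and vital-status collection to 12 months, by telephone or through the dialysis-center and treating-physician route that Section 12 and Appendix A already allow.
2. Sections 7.2 and 7.3: align them with each other and with 7.1, so that such a subject does not count as discontinued for safety.
3. Section 9: state that related AEs are reported over all treated subjects, with the follow-up time given.
4. Leave withdrawal initiated by the subject or the investigator as it is. Limiting withdrawal to withdrawn consent would remove the investigator's right in Section 6, which is not the problem here.

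Cost: edits to these sections, consent wording for continued safety contact, and a few remote contacts for each affected subject. No procedure is added.

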7 ADVERSE EVENTS

7.1 Definitions

Adverse Event (AE)

An adverse event (AE) is any untoward medical occurrence in a subject (regardless of treatment group) that may or may not have a causal relationship with the study procedure. An AE therefore can be any unfavorable or unintended sign (including a clinically significant abnormal laboratory finding, for example), symptom, or disease temporally associated with the use of a medicinal product or procedure, whether or not considered related to the product or procedure. A serious adverse event (SAE) is any untoward medical occurrence that meets any of the criteria for an SAE as defined below.

Subjects should be instructed to report any AE that they experience to the Investigator or Study Coordinator. Adverse events (AE) will be collected starting on the date of study procedure. AEs will be re-assessed at 30 days, 3 months, 6 months, and 12 months, and at any additional interim visit. AEs occurring during the study procedure and the protocol-defined 12 month follow-up period should be recorded on the appropriate AE CRF. It is important that the Investigators record AE terms accurately and consistently throughout the study. Wherever possible, a specific disease or syndrome should be reported

on the CRF rather than the associated individual signs and symptoms (e.g., diabetes mellitus instead of hyperglycemia). If observed or reported signs or symptoms are not considered a component of a specific disease or syndrome by the Investigator, they should be recorded as separate AEs on the CRF. For this study venous outflow obstructions will not be considered adverse events because they will be captured in the calculation of Assisted Primary Patency of the target lesion, Assisted Primary Patency of the venous outflow circuit, and Index of Patency Function.

Serious Adverse Event (SAE)

A serious adverse event (SAE) is any adverse event, regardless of causality that:

- Results in death
- Is life-threatening, where life-threatening means that the subject was at immediate risk of death from the reaction as it occurred, i.e., it does not include a reaction which hypothetically might have caused death had it occurred in a more severe form.
- Requires in-patient hospitalization or prolongation of existing hospitalization. Hospitalization admissions and/or surgical operations scheduled to occur during the study period, but planned prior to study entry are not considered AEs if the illness or disease existed before the subject was enrolled in the trial, provided that it did not deteriorate in an unexpected manner during the trial e.g., surgery performed earlier than planned.
- Results in persistent or significant disability/incapacity, where disability is defined as a substantial disruption of a person's ability to conduct normal life functions.
- Is a congenital anomaly/birth defect
- Is an important medical event as defined by the Investigator. An important medical event is an event that may not result in death, be life-threatening, or require hospitalization, but may be considered an SAE when, based upon appropriate medical judgment, it may jeopardize the subject and may require medical or surgical intervention to prevent one of the outcomes listed in the definitions for SAEs. Examples of such medical events include allergic bronchospasm requiring intensive treatment in an emergency room or at home, blood dyscrasias or convulsions that do not result in subject hospitalization, or the development of drug dependency or drug abuse.

Clarification should be made between the terms “serious” and “severe” since they are not interchangeable. The term “severe” is often used to describe the intensity of a specific event (as in mild, moderate, or severe myocardial infarction); the event itself, however, may be of relatively minor medical significance (such as a severe headache). This is not the same as “serious,” which

is based on the subject/event outcome or action criteria described above and are usually associated with events that pose a threat to a subject's life or functioning. A severe adverse event does not need to be considered serious. For example, persistent nausea of several hours duration may be considered severe nausea but not constitute a SAE, unless the subject would be admitted to the hospital or the event would meet any other of the criteria for seriousness. On the other hand, a stroke resulting in only a minor degree of disability may be considered mild, but would be defined as an SAE based on the above noted criteria. Seriousness (not severity) serves as a guide for defining regulatory reporting obligations.

Under this protocol, scheduled hospitalizations or elective surgical procedures will not be considered SAEs. Deaths due to renal disease progression will not be considered SAEs.

Unanticipated Adverse Device Effect (UADE)

An unanticipated adverse device effect (UADE) is any serious adverse effect on health or safety, any life-threatening problem or death caused by, or associated with a device, if that effect, problem, or death was not previously identified in nature, severity, or degree of incidence in the application; or any other unanticipated serious problem associated with a device that relates to the rights, safety, or welfare of subjects.

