2 STUDY OBJECTIVES

2.1 Primary Objectives

Safety

- Proportion of subjects without any localized or systemic safety events through 30 days that affect the access or venous outflow circuit and resulted in surgery, hospitalization, or death
 - Safety events in this calculation will not include venous outflow obstructions, which are captured in the calculation of Assisted Primary Patency of the target lesion, Assisted Primary Patency of the venous outflow circuit and Index of Patency Function

Effectiveness

- Proportion of subjects with Target Lesion Primary Patency at 30 days
 - Time to loss of Target Lesion Primary Patency is defined as the time interval of uninterrupted patency from initial study procedure to the next intervention performed on the target lesion or uncorrectable target lesion occlusion, whichever occurs first

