8 DATA MONITORING/CLINICAL EVENTS COMMITTEE & SAFETY STOPPING RULES

A Data Monitoring/Clinical Events Committee (DMC/CEC) will be formed consisting of at least 3 individuals with expertise and experience in clinical trials, and safety evaluations, but without direct involvement in the conduct of the study. The exact responsibilities, procedures, and guidelines used to manage the DMC/CEC are described in a separate charter.

Any SAE or UADE resulting in surgery or death will trigger a DMC/CEC meeting. The study will stop at 1 SAE or UADE unless the DMC/CEC determines that the event was not primarily due to the study device or procedure. The DMC/CEC will review and adjudicate all target lesion and access circuit interventions performed after the study procedure.

In addition, termination or modification may be recommended for any other perceived safety concern based on clinical judgment of the DMC members.

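### Section 7.1 exempts all scheduled admissions and elective surgery from SAE status, without its own planned-before-entry condition, so some device problems could miss expedited reporting and the Section 8 triggers

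*Combined protocol and SAP*

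**What the plan says.** Section 7.1 contains two exemptions.

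- **Conditional.** Within the SAE criterion "Requires in-patient hospitalization or prolongation of existing hospitalization", the text adds: "Hospitalization admissions and/or surgical operations scheduled to occur during the study period, but planned prior to study entry are not considered AEs". This holds only where the illness pre-dated enrollment, and "provided that it did not deteriorate in an unexpected manner during the trial e.g., surgery performed earlier than planned".
- **Unconditional.** After the discussion of serious versus severe, and just before the UADE definition, the section states: "Under this protocol, scheduled hospitalizations or elective surgical procedures will not be considered SAEs". It sets no limit on when the event was planned, why, or whether the condition worsened.

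SAE status then drives other rules. Section 7.3 requires a 24-hour report of any SAE or unanticipated adverse event. Section 8 says: "Any SAE or UADE resulting in surgery or death will trigger a DMC/CEC meeting". It also halts the study at one SAE or UADE unless the DMC/CEC finds that the event was not mainly due to the device or procedure. Separately, Section 8 has the DMC/CEC adjudicate every target lesion and access circuit intervention after the study procedure.

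The primary safety endpoint (Sections 2.1, 4 and 9) counts 30-day safety events "that affect the access or venous outflow circuit and resulted in surgery, hospitalization, or death". It excludes venous outflow obstructions.

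**The concern.** An operation booked after implantation because of a device problem fails the conditions of the first exemption but falls within the second. The second comes later and is phrased as a rule for this protocol, so a site could fairly treat it as controlling.

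This is a first-in-human device study with a stopping threshold of one event, so the classification of a single event can decide whether the stopping rule is engaged. Surgery is also one of the two outcomes that trigger a committee meeting, yet the broad sentence takes elective surgery out of SAE status. Whether an event is scheduled or an emergency says little about whether the device caused it.

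**Working it through.** No figure in the plan bears on this point, so the check sets the rules side by side and follows one case through them.

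**Test case.** After implantation, a subject develops an anticipated device or procedure problem that is not an obstruction (infection or bleeding would be examples; these are mine, not the protocol's). It is managed by a scheduled in-patient admission or an elective operation.

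1. **Conditional exemption (7.1).** The event was not planned before entry, so it is not exempt, and an in-patient admission meets the hospitalization criterion for an SAE.
2. **Unconditional exemption (7.1).** The event is scheduled or elective, so it is not an SAE. Steps 1 and 2 give opposite answers.
3. **24-hour report (7.3).** If step 2 governs, the SAE route is closed. The unanticipated-event route is closed too, because the problem was anticipated.
4. **Automatic meeting and one-event stop (8).** Both need an SAE or a UADE. A UADE must not have been identified beforehand in nature, severity or incidence, so an anticipated problem does not qualify. Neither trigger operates.
5. **Other SAE criteria (7.1).** The broad sentence names the admission or procedure, not the underlying event. That event can still be serious if it is life-threatening or disabling, or if it is an important medical event because "it may jeopardize the subject and may require medical or surgical intervention to prevent one of the outcomes listed in the definitions for SAEs". The last of these rests on the investigator's judgment.
6. **Adjudication (8).** If the operation is on the target lesion or access circuit, the DMC/CEC adjudicates it whatever its SAE status. Section 8 gives no timing for this and does not tie it to the meeting trigger. A scheduled admission without such an intervention is not covered.
7. **Recording and endpoint (7.1, 9).** The underlying event remains an AE and goes on the AE form. Through 30 days it can still count in the primary safety endpoint, which is not defined through SAEs.
8. **Obstruction (7.1).** If the problem is a venous outflow obstruction, it is not an AE at all under a separate rule, and the broad sentence plays no part.

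The protocol handles a comparable exclusion differently. Deaths from disease progression are not SAEs, but Section 7.2 still requires them to be reported within 24 hours on a Death Report form. Scheduled admissions and elective surgery have no such substitute.

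**The case against.** The strongest reply is that the broad sentence merely abbreviates the conditional one. The two also address different classifications: the conditional text removes events from AE status, the broad one from SAE status only. Surgery alone is not a listed SAE criterion, so an elective operation without admission would depend on the remaining criteria even if the sentence were deleted. Unanticipated events and UADEs keep their own triggers.

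Most of this stands, and it narrows the gap. It does not remove the gap, because nothing in the text ties the broad sentence to the earlier conditions, and the test case above passes through every backstop except investigator judgment and, for some operations, adjudication.

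Two stronger readings are tempting and should not be adopted.

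- **That such events escape committee review.** Section 8 sends all target lesion and access circuit interventions to adjudication regardless of SAE status. For those, what can be lost is the automatic meeting and the stopping trigger, not review.
- **That the 30-day safety proportion is inflated.** With about 50 subjects, each one is worth 1/50 = 2 percentage points, so a shift is easy to imagine. But no rule drops an event from the endpoint because it is not an SAE, and nothing says the endpoint is ascertained mainly from SAE forms. AE review and interventions since the last visit are collected at the 30-day visit (Section 5, Appendix A), and sites check with dialysis centers for revisions done elsewhere (Section 12).

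**Conclusion.** The inconsistency within Section 7.1 is real and should be reconciled. Its reach is limited to admissions or elective operations first scheduled after implantation, for an anticipated, non-obstructive device or procedure problem that is not judged serious on another criterion. For those, a literal reading can lose the 24-hour SAE report, the automatic DMC/CEC meeting and the one-event stopping rule.

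The documents do not say how many such events to expect, so the size is stated as the set of rules affected rather than as a number. The conclusion assumes that a site applies the broad sentence as written; it does not assume any intent to avoid reporting. No effect on the primary safety proportion is claimed.

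**What to change.** In Section 7.1, limit the broad sentence to the conditions the section already sets: planned before study entry, for a pre-existing condition, with no unexpected deterioration. Add that any other admission or operation scheduled after the study procedure is assessed against the ordinary SAE criteria. State that the separate exclusion of venous outflow obstructions is unchanged. Without that, the addition could be read as bringing surgery for obstruction into SAE reporting and the stopping rule, in conflict with Sections 2.1, 4, 7.1 and 9.

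The cost is an edit of one or two sentences, the written EC approval that Section 12 requires for changes that may affect safety, a few more SAE forms, and possibly more DMC/CEC meetings.
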